## 11. Power Analysis:

A power analysis was conducted using our preliminary data examining a cohort of 50 unmedicated patients with major depression.[27] The study sample size was powered on the basis of Aim 1, which represents the primary hypothesis of the study that riluzole will decrease basal ganglia glutamate. Given a sample size of 40, an alpha of 0.05, a power of 0.80, we will be able to detect an effect size of Cohen's  $d=0.5$  which falls in the moderate range (computed using G\*power). This effect size is well within the range of the effect size ( $d$ ) of the differences in basal ganglia glutamate concentrations between high (CRP>3mg/L) and low (CRP<1mg/L) inflammation, which are expected in this study.

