Thus, CNS glutamate may serve as a final common pathway to CNS pathology and behavioral and cognitive disturbances in breast cancer patients after treatment. Interestingly, memantine, a drug that antagonizes glutamate signaling was found to preserve cognition in cancer patients undergoing whole brain radiotherapy, indicating that blocking glutamate may have neuroprotective effects under conditions of an increased inflammatory load. Taken together, these data suggest that glutamate may be an outstanding target for reversing the behavioral pathology associated with inflammation during breast cancer and its treatment. Demonstration that targeting glutamate to reverse fatigue and cognitive changes in patients with high inflammation and could potentially help treat the long-term toxicities of breast cancer and its treatment. The goal of the current proposal is to test the hypothesis that reduction of glutamate in breast cancer survivors with fatigue and high inflammation will be associated with decreased CNS glutamate and decreased symptoms of fatigue and cognitive function including anhedonia and psychomotor slowing. To test these hypotheses the following aims are proposed:

**Aim 1: To study the impact of 8 weeks of riluzole treatment on CNS glutamate concentrations in breast cancer patients with increased fatigue and high inflammation.**

Using a double-blind randomized controlled trial design, 40 female breast cancer patients with increased fatigue ( $\geq 4$  on a 10 point scale) and high inflammation (CRP $>3$ mg/L) will be treated for 8 weeks with either riluzole or placebo (n=20 per group). At baseline and at 1 and 8 weeks of treatment, all subjects will undergo single voxel MRS to measure CNS glutamate. Voxels will be placed in the right and left basal ganglia and the dACC. In addition, chemical shift MRS imaging will be employed to explore potential glutamate changes in other brain regions of interest.

**Hypothesis 1:** Breast cancer patients administered riluzole will exhibit greater decreases in basal ganglia and dACC glutamate compared to women treated with placebo.

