## **6. Study design and methods:**

### **Participant Selection**

Breast cancer research participants will be referred by physicians in the Glenn Family Breast Center at Winship Cancer Institute of Emory University, recruited through social media campaigns, or recruited through letters from the Georgia Center for Cancer Statistics. We plan to enroll 120 female breast cancer patients between the ages of 21-65 inclusive (to obtain 40 patients with analyzable data). All breast cancer patients will have completed surgery (lumpectomy or mastectomy) with or without neoadjuvant or adjuvant chemotherapy and with or without radiation between 1-5 years prior to enrollment.

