### **Participants**

40 female patients with Stage I-III breast cancer that are between 1-5 years post treatment and are between the ages of 21 and 65, unless otherwise approved by the PI, will be enrolled in this clinical trial. Participants will have completed surgery (lumpectomy or mastectomy) with or without neoadjuvant or adjuvant chemotherapy and with or without radiation. Subjects must have a CRP > 3mg/L and a Single Item Screening Scale for Fatigue score of  $\geq 4$  (out of 10 points, 0 being no fatigue and 10 being severe, incapacitating fatigue) to be eligible for the trial. Based on projections that ~50% of recruited subjects will have a CRP > 3mg/L and a Fatigue score  $\geq 4$  and ~20 of subjects will drop out during the clinical trial, we anticipate that we will need to recruit 120 subjects to yield analyzable data for 40 breast cancer subjects. No patients will be enrolled from vulnerable populations, including neonates, children, prisoners, or institutionalized individuals. No use will be made of fetal tissue. Potential subjects will be excluded for a number of medical conditions that might represent a risk for riluzole (including history of allergic reaction to riluzole and evidence of liver disease) and potentially confound the relationship among CNS glutamate, inflammation and behavior/cognition, including autoimmune or inflammatory disorders, chronic infectious diseases (e.g. HIV, hepatitis B or C), pregnancy, neurologic disorders (including a history of serious head trauma or seizures), liver disease (as manifested as an elevation in liver transaminases) and uncontrolled cardiovascular, metabolic, pulmonary or renal disease (as determined by medical history and laboratory testing). Subjects with a current or past history of schizophrenia will also be excluded. Subjects with Bipolar Disorder that have experienced a manic episode within 6 months of study entry will be excluded or at the PI's discretion. Subjects receiving antidepressants, mood stabilizers, antipsychotic medications or

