**Riluzole Flowchart:**

### **Randomization**

Subjects will be randomized to 100 mg of riluzole (50 mg po BID) or an identical appearing placebo in a 1:1 fashion with no stratification. Subjects will be instructed to take the study medication on an empty stomach (1 hour before or 2 hours after meals). The dosage of riluzole is based on several clinical trials that have previously used this medication to treat a number of psychiatric disorders ranging from depression to generalized anxiety disorder as well as ALS.[31] A randomly generated sequence of assignments to riluzole or placebo will be created and maintained by the study pharmacist. Subjects will be randomized in blocks of 4. If a subject drops out prior to receiving the first dose of medication, she will not be included in data analyses and her randomization assignment will “roll over” to the next recruited subject until 40 subjects have received at least one dose of medication or placebo.

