## 10. Statistical Analysis:

**Aim 1: To study the impact of 8 weeks of riluzole treatment on CNS glutamate concentrations in breast cancer patients with increased fatigue and high inflammation.**

**Hypothesis 1:** Breast cancer patients administered riluzole will exhibit greater decreases in basal ganglia and dACC glutamate compared to women treated with placebo.

Mixed-effects models for repeated measures (MMRM) will be employed to examine effects of group, time and their interaction on left and right basal ganglia glutamate or dACC controlling for baseline glutamate concentrations in separate analyses for each brain region. Relevant covariates including age, sex, race (white/non-white) and body mass index (BMI), socioeconomic status (as measured by household income), educational status, tumor stage, tumor receptor status (where appropriate), timing (adjuvant versus neoadjuvant) of chemotherapy and radiation (yes/no) will be sequentially tested in the models for goodness of fit (Akaike Information Criterion) and included as appropriate.

**Aim 2: To determine whether decreased CNS glutamate correlates with improved symptoms of fatigue and cognition dysfunction.**

**Hypothesis 2:** Decreased glutamate in the basal ganglia will be associated with decreased fatigue and improved motivation and processing speed. Decreased glutamate in the dACC will be associated with improved executive function and memory performance.

Random intercept linear mixed models will be used to assess whether change in left or right basal ganglia or dACC glutamate predict change in fatigue scores or change in neurocognitive function over time. Models will be adjusted for relevant clinical covariates (including IDS-SR, PSQI, BAI) as indicated above. Separate analyses will be run for each behavioral outcome (MFI, PROMIS) as well tests of cognition (HVLT-R, TMT PASAT COWAT RT FTT, RTT, and DSST) and motivation (DDT, EEfRT, Subjective Value Task, Effort and Delay Task, Daily Assessment/Mobile App Task, Gamble Task, and Go No-Go Variant Task.). Type I errors as a result of multiple testing will be controlled by using a step down Bonferroni procedure.[68]

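### The claim of 80% power at d = 0.5 with 40 women does not reproduce for riluzole versus placebo; at 20 per arm, unadjusted two-sided power is about 34%

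*Combined protocol and SAP*

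**What the plan says.** Section 11 (Power Analysis) says the study was sized on Aim 1, named there as the primary hypothesis, that riluzole lowers basal ganglia glutamate. It continues: "Given a sample size of 40, an alpha of 0.05, a power of 0.80, we will be able to detect an effect size" of Cohen's d = 0.5, computed in G*Power. It names no test, visit, sidedness, standard deviation or correlation. It supports d = 0.5 by reference to "differences in basal ganglia glutamate concentrations between high (CRP>3mg/L) and low (CRP<1mg/L) inflammation, which are expected in this study", taken from a cohort of patients with depression.

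Four other places bear on this:

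- **Design.** Section 5, Aim 1: the women "will be treated for 8 weeks with either riluzole or placebo (n=20 per group"), with MRS at baseline, Week 1 and Week 8.
- **Analysis.** Section 10: a mixed model for repeated measures with group, time and their interaction, "controlling for baseline glutamate concentrations in separate analyses for each brain region".
- **Eligibility.** Section 6, Participants: "Subjects must have a CRP > 3mg/L".
- **Meaning of 40.** Section 6, Participant Selection, plans enrolment "to obtain 40 patients with analyzable data". Participants allows that about "20 of subjects will drop out during the clinical trial". Randomization continues "until 40 subjects have received at least one dose of medication or placebo".

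**The concern.** A total of 40 is small for a between-group standardised difference of 0.5, so the first question is whether the stated power belongs to the comparison the trial makes. This sentence is the only justification given for the sample size. If it is wrong, a null Aim 1 result will be read as evidence against a moderate effect that the trial had a poor chance of detecting. Two further points weaken the sentence. Its benchmark is a contrast between inflammation groups, one of which the trial does not enrol. And the 40 it uses may be a count before or after dropout.

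**Working it through.** **Inputs.** 20 per arm (Section 5); alpha 0.05, power 0.80 and d = 0.5 (Section 11); baseline adjustment (Section 10); scans at baseline, Week 1 and Week 8 (Section 5). Sidedness is not stated, so both are shown. The baseline-to-follow-up correlation ρ is not stated and is assumed over a range. Throughout, d is in units of the raw between-woman SD at a single visit.

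**1. The plan's own figure, as a two-group comparison.** Noncentral t with df = 38 and noncentrality d·√(n/2) = 0.5 × √10 = 1.58. The critical values are 2.02 (two-sided) and 1.69 (one-sided).

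| 20 per arm, unadjusted, one visit | Power at d = 0.5 | d detectable at 80% | n per arm for d = 0.5 |
|---|---|---|---|
| Two-sided | 0.338 | 0.909 | 64 |
| One-sided | 0.463 | 0.801 | 51 |

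Reading 40 as the number per arm gives 0.598 two-sided and 0.716 one-sided. None of these is 0.80.

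**2. The planned baseline adjustment.** Adjustment multiplies the variance of the treatment contrast by a factor V, so the noncentrality becomes (d/√V)·√(n/2).

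- Week 8 alone: V = 1 − ρ².
- Mean of Weeks 1 and 8: V = (1 + ρ)/2 − ρ². This assumes one common correlation among the three scans and the same effect at both visits.

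For example, ρ = 0.7 gives V = 1 − 0.49 = 0.51 and V = 0.85 − 0.49 = 0.36.

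| ρ (assumed), two-sided | Week 8: power at d = 0.5; detectable d | Mean of Weeks 1 and 8: power at d = 0.5; detectable d |
|---|---|---|
| 0.5 | 0.43; 0.79 | 0.59; 0.64 |
| 0.7 | 0.58; 0.65 | 0.73; 0.55 |
| 0.8 | 0.73; 0.55 | 0.86; 0.46 |

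Using df = 37 for the covariate changes these by at most 0.001.

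**3. Correlation needed for 80% power at d = 0.5.** Two-sided, V must fall to 0.302. Then √(1 − 0.302) = 0.835 for Week 8, and solving (1 + ρ)/2 − ρ² = 0.302 gives 0.760 for the mean of the two scans. One-sided, V must fall to 0.390, giving 0.781 and 0.665.

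**4. Other ways to arrive at 40.**

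- A paired or one-sample t-test on all 40 women has power 0.869 at d = 0.5, but it does not compare riluzole with placebo.
- A repeated-measures group-by-time interaction with f = 0.25, three measurements and N = 40 has power 0.799 at a correlation of 0.25. This may be where the figure came from. It also needs an unstated correlation, and f = 0.25 is a different effect. With two time points it means ±0.25 SD in each of four cells, a group difference in change of 4 × 0.25 = 1.0 raw SD.
- If d is already in change-score SD units, the gain from correlation is used up and power stays near 0.34.

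**5. Benchmark.** Section 11 cites the gap between CRP above 3 mg/L and CRP below 1 mg/L. Eligibility admits only the first group, so the second does not exist in this trial. The gap is also a cross-sectional difference between patients, not a difference between treatments.

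**6. Which 40.** 120 × 0.5 = 60 eligible. Taking the dropout figure of about 20 as a count leaves 60 − 20 = 40; taking it as a percentage leaves 60 × 0.8 = 48. Randomization, however, stops at 40 dosed, so any loss after the first dose takes the analysable number below 40. As an example only, 20% loss from 40 dosed leaves 32 (16 per arm): unadjusted two-sided power 0.278 and detectable d 1.02 among completers.

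**The case against.** The strongest reply is that 34% describes an analysis nobody plans. Section 10 specifies baseline adjustment with two follow-up scans, and the powered hypothesis is directional. One-sided, with both scans averaged and ρ = 0.7, power at d = 0.5 is 0.827 and the detectable d is 0.480, which meets the Section 11 figure. The two-sided averaged analysis gets there at ρ = 0.8. Section 10 also allows other covariates. If they removed an assumed 20% of the remaining variance, the two-sided thresholds would fall to about 0.79 and 0.68. A Week 1 to Week 8 correlation of 0.5 with a baseline correlation of 0.7 gives V = 0.75 − 0.49 = 0.26 and averaged two-sided power of about 0.86.

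All of this stands as arithmetic: 80% power is possible. But each route rests on a correlation, a sidedness or a covariate gain that the documents never state, so none supports the sentence as written.

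Two smaller points also have some force. The CRP gap could serve as a loose benchmark, since the background argues that inflammation raises glutamate and riluzole may lower it; even so, it cannot be an effect expected in this trial. The missing unit on the dropout figure may be a character lost in text extraction, and the funnel arithmetic favours a count. The conflict between 40 analysable and 40 dosed does not depend on it.

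**Conclusion.** The power statement is wrong as written. For riluzole versus placebo at 20 per arm, 80% power at d = 0.5 is not what N = 40 gives without further assumptions. An unadjusted two-sided comparison at one visit would miss a true d = 0.5 about 66% of the time. The baseline-adjusted analysis, two-sided and at assumed correlations of 0.5 to 0.7, would miss it about 42–57% of the time at Week 8 and 27–41% of the time averaging both visits. At ρ = 0.8 the miss rates fall to about 27% and 14%. The unadjusted figures need only the stated n and alpha. The adjusted ones rest on the assumed correlation and, for the average, on a common correlation and equal effects at both visits. No allowance is made for testing three brain regions. The CRP benchmark does not apply, and the documents do not settle whether 40 is before or after dropout.

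**What to change.** Restate Section 11 along these lines, with d in raw SD units:

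- With 20 analysable women per arm, two-sided alpha 0.05 and 80% power, the detectable riluzole-placebo difference is d of about 0.91, unadjusted at one visit.
- With baseline adjustment at Week 8 it is about 0.79 if ρ = 0.5 and 0.65 if ρ = 0.7. Averaging Weeks 1 and 8 it is about 0.64 and 0.55, assuming a common correlation and the same effect at both visits.
- State the test, visit, SD and correlation used. If a one-sided test was intended, say so and give the one-sided figures instead.
- Remove the high-versus-low CRP difference as an effect expected in this trial.
- Reconcile 40 analysable (Participant Selection) with 40 dosed (Randomization), and give the unit of the dropout figure. If 40 means dosed, restate the detectable effect for the expected analysable number. The 16-per-arm example gives about 1.02 unadjusted; the mixed model would lose less, because it keeps women who have only a Week 1 scan.

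The cost is protocol wording and a less favourable stated detectable effect. No extra patients are needed.

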## 12. Potential Study Risks:

**Main Riluzole Study Risks:** There are 4 major areas of potential risk in the proposed study stemming from 1) neuropsychiatric assessments, 2) blood drawing, 3) MRS scanning and 4) riluzole treatment. Neuropsychiatric assessments may uncover unpleasant feelings about the subject's present emotional state. The risks of blood drawing include discomfort, bruising, infection, bleeding and fainting. Undergoing MRS scan poses no more risk than undergoing a routine MRI scan. Nevertheless, physical discomfort due to lying in the scanner, occasional headaches due to scanner sounds and previously unrecognized claustrophobic attacks are the

prominent adverse effects of the procedure. Major complications of riluzole (Rilutek) include an allergic reaction to riluzole or the components of the tablet and hepatic toxicity. Riluzole is contraindicated in individuals who have a history of hypersensitivity reactions to riluzole or any of the tablet components and in individuals who have hepatic disease or who have baseline transaminases greater than 3 times the upper limit of normal. The drug is also contraindicated in women who are pregnant. Subjects of childbearing ability must agree, with the study doctor or PI's designee, on a method of birth control to use throughout the study. To ensure no contraindications with alcohol, participants will be told not to consume more than 1 alcoholic drink per day while on study medication (12 fl oz of beer, 5 fl oz of wine, 1.5 fl oz shot of distilled spirit, and also not to consume any alcohol within 24 hours of a study visit brain scan. Of the most commonly observed adverse events associated with the use of RILUTEK in 1,396 individuals with amyotrophic lateral sclerosis, those reported more frequently than with placebo treatment were: asthenia, nausea, elevations in liver function tests, dizziness, decreased lung function, diarrhea, abdominal pain, pneumonia, vomiting, vertigo, circumoral paresthesia, anorexia and somnolence. Table 2 shows the most common treatment-emergent adverse reactions considered possibly related to medication and for which the incidence was  $\geq 1\%$  in an open label Phase IV confirmatory trial for amyotrophic lateral sclerosis of 414 patients.

### **Startle Study Risks:**

The most common risks and discomforts expected in this study are:

Risks associated with interviews: Psychological tests and interviews can sometimes bring up painful emotions. These emotions may include sadness, worry, or increased anxiety. If you have trauma-related stress symptoms, you may have an increase in nightmares or flashbacks related to your traumatic experiences. You are free not to answer any questions you wish. You may stop participating in the study at any time. This will not in any way affect your future care.

Risks associated with the acoustic startle test: During the startle measurement, scrubbing your skin with cleanser or application of skin tape may cause skin irritation. The noise level you will hear during the startle test session is about what you hear on a train. For most people, this sound level is not uncomfortable. If the sounds or airblasts cause you discomfort, you can stop the test session at any time. Withdrawal from the study will not affect your future care. There also may be unknown risks, discomforts or side effects

The less common risks and discomforts expected in this study are:

Risks associated with the psychophysiological procedure: You may become tired from sitting in front of the computer, or may become uncomfortable sitting in one position for a long period of time. You can take a break at any point during these tasks and you can stop at any point during the visit.

Risks associated with the saliva collection: You may feel uncomfortable producing saliva and spitting into the collection tube. You are free to take as long as you need for this process, you can take a break at any point, or discontinue the process if you wish.

**Table 2 -The most common treatment-emergent adverse reactions (TEAR) considered possibly related to study medication occurring in study 401 and for which the incidence was  $\geq 1\%$**

System Organ Class	Preferred Term	Studies 401 (N=414) %
Gastrointestinal Disorders	Nausea	6
	Stomach discomfort	3
	Diarrhea	2
	Dyspepsia	1
	Constipation	1
	Hypoaesthesia oral	1
General Disorders and Administration Site Conditions	Fatigue	4
Nervous System Disorder	Dizziness	4
	Headache	1
	Dysgeusia	1
Psychiatric Disorders	Insomnia	1
Skin and Subcutaneous Tissue Disorders	Rash	1
	Pruritus	1
Hepatobiliary Disorders*	Alanine aminotransferase (ALT/SGPT) abnormal	1

\* Alert terms (ALT and/or AST values  $>10$  times the upper limit of normal) or abnormal values that led to study drug termination

At screening, study clinicians will discuss benefits and risks of study participation. Alternatives include not participating in the proposed study.

**Adequacy of Protection Against Risks**

Protection Against Risk:

Every effort will be taken to prevent injury or distress that may result from this study. Care will be taken to avoid bringing about undue psychological distress during the self-reported questionnaires. In the event that a subject becomes unduly distressed or scores  $>32$  on the IDS-SR (indicating moderate to severe depressive symptoms) or endorses a score  $>2$  on the suicide item of the IDS-SR (Question 18) or a score  $\geq 3$  on the PHQ-9 suicide item, the PI or his designee will be immediately contacted, and an appropriate clinical intervention plan will be developed. Emory has inpatient, outpatient and emergency room psychiatric services at all recruitment and evaluation sites. In addition, the PI [name] is a Board-certified psychiatrist and has extensive experience in administering standardized clinical assessments and handling psychiatric emergencies. As for blood drawing, standard sterile procedure for blood withdrawal will be used. Blood draws will be conducted by trained phlebotomists with

significant experience in the technique. In addition, the volume of blood withdrawn for this study will not exceed 40 mL over the course of the study (including screening and assessment visits). To minimize discomfort during the MRS scanning, patients will be provided with a head cushion and earplugs. Patients will also be informed about the progress of the procedure through a remote microphone. In the case of patients developing acute anxiety or panic, the scanning session will be terminated and patient provided enough support to cope with the feelings induced by the scanner. If a patient is uncomfortable with the skin cleansing during the psychophysiological task, it will be omitted. Patients will be told about the airblast prior to beginning the task. If they are uncomfortable with this or any part of the task, the task will be stopped. To reduce the likelihood of adverse reactions to riluzole, all patients will have a thorough history of allergic reactions reviewed and their first dose of riluzole will be administered under supervision of a study physician or nurse practitioner. In addition, all patients will be screened for evidence of liver disease including a screen for liver transaminases as well as hepatitis B and C and HIV. Liver transaminases will also be monitored at weeks 4 and 8, and subjects will be instructed to inform staff of any gastrointestinal symptoms.

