### **Description of Study Procedures (Baseline 1, Startle Study, Baseline 2 and Weeks 1-8)**

All eligible participants with a CRP>3mg/L and a Fatigue Score  $\geq 4$  will complete Baseline 1, be randomized to receive riluzole (100 mg/d) or placebo at Baseline 2, and proceed to study visits at Weeks 1, 2, 4, and 8.

During the Baseline 1 visit and on Week 1 and Week 8, subjects will undergo magnetic resonance spectroscopy (MRS). Between baseline 1 visit and baseline 2 visit, participants will have the option of undergoing a parallel Startle Test Study protocol. This protocol will consist of either 1 or 2 visits, for completing psychiatric assessments and self-report forms and for completing a psychophysiological startle task. A schedule of all assessments is provided in Table 1. Approximately 30 mL of blood will be drawn at the same time of day between 8-10AM (to reduce potential circadian effects) under sterile conditions at Baseline 1 and 2 and Weeks 1, 4 and 8. Screening/safety labs are not time dependent. Safety labs will be completed at Baseline 2, Week 4 and Week 8. At each visit, self-report forms with urine toxicology will occur as well as recording of concomitant medications and adverse events. Neurocognitive testing will be completed on Baseline 1, Baseline 2 and Week 8. Where indicated, participants will be administered the neurocognitive tests and the scanning sequence of the MRS will be completed based on scanner availability and at the discretion of the PI or PI's designee. Subject will be read MRI instructions 48hrs prior to Baseline 1, Week 1, and Week 8 visits to have the subject avoid specific foods, medications, alcohol and cigarettes starting 24hrs prior to the MRS scan. A light lunch/snack may be provided after the fasting lab work.

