**Table 1. Schedule of Study Procedures and Assessments**

Procedures for MRS Controls	Intake	Screen Visit	Baseline 1 +	Startle Study (optional)	Baseline 2 + (randomization)	Week 1 +	Week 2 +	Week 4 +	Week 8 +
Informed consent	X								
Screening/ Safety labs*		X			X			X	X
Psychiatric Assessments*, **		X		X					
Medical History and Physical		X							X
Concomitant Medications		X	X	X	X	X	X	X	X
Adverse Events		X	X	X	X	X	X	X	X
MRI Safety Form		X							
Demographics		X							
Startle Task**				X					
Research Blood*			X		X	X		X	X
Urine toxicology (Test kit)		X	X		X	X		X	X
Self-Report Forms*, **			X	X	X	X	X	X	X
Neurocognitive Tests*			X		X				X
MRI Scan Food, Drink and Cigarette Intake Forms			X			X			X
MRS			X			X			X
Placebo or Riluzole (100mg/d)					X	X	X	X	X

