**+ - for patients with a CRP>3mg/L and a Single Item Screening Scale for Fatigue Score ≥4**

**\* - for patients completing the main branch of the Riluzole Study**

**\*\* - for patients who opt for to complete the Startle Test Study**

**Key:**

**Main Riluzole Study**

\*Screening/ Safety Labs: CBC w/Diff, Metabolic Panel, hCG quantitative serum, TSH, Urinalysis w/micro at Screening and Week 8 only, Urine drug test all visits (test kit), except week 2 visit; Testing for CRP, Hepatitis B and C and HIV will be conducted on the screening visit only, unless otherwise approved by the PI. A Rapid C Reactive Protein finger prick may also be obtained by trained research staff using a rapid CRP finger prick test at the discretion of the investigator to expedite determining eligibility for research participation.

\*Psychiatric Assessments: WRAT-3, MMSE, CTQ, QID-S, Single Item Screening Scale for Fatigue

\*Research Blood: Cytokine Multiplex, TRP, KYN, mRNA analysis, methylation analysis, and gene analysis (collected under fasting conditions)

\*Self-Report Forms: IDS-SR, MFI, PROMIS-Fatigue, BAI, PSQI, Assessment of Pain level, PHQ-9, Single Item Screening Scale for Fatigue, Baycrest Memory Scale

\*Neurocognitive Tests:

Baseline 1 - EEfRT, Finger Tapping Task (FTT), The Trail Making Test (TMT), Digit Symbol Task, Reaction Time Task (CANTAB)

Baseline 2 - Rey Auditory Verbal Learning Test (RAVLT), Delayed Matching To Sample (CANTAB), Spatial Working Memory (CANTAB), Stroop Color and Word Test

Week 8- EEfRT, Finger Tapping Task (FTT), The Trail Making Test (TMT), Digit Symbol Task, Reaction Time Task (CANTAB), Rey Auditory Verbal Learning Test (RAVLT), Delayed Matching To Sample (CANTAB), Spatial Working Memory (CANTAB), Stroop Color and Word Test

[figure not shown]

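### The stated 40 mL limit on blood for the whole study and the schedule of about 30 mL at five visits cannot both be followed

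*Combined protocol and SAP*

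**What the plan says.** Three places in the combined protocol and SAP bear on blood volume.

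- **Section 12, Adequacy of Protection Against Risks.** The volume withdrawn "will not exceed 40 mL over the course of the study (including screening and assessment visits"). This is worded as a maximum for the whole study, and screening is expressly inside it.
- **Section 6, Description of Study Procedures.** "Approximately 30 mL of blood will be drawn at the same time of day between 8-10AM", and the same sentence places the draw "under sterile conditions at Baseline 1 and 2 and Weeks 1, 4 and 8". The section adds that "Safety labs will be completed at Baseline 2, Week 4 and Week 8".
- **Table 1 and its key.** The row "Research Blood" carries five marks, at the same five visits. The row for screening and safety labs carries four: the screening visit, Baseline 2, Week 4 and Week 8. The key says "Testing for CRP, Hepatitis B and C and HIV will be conducted on the screening visit only", subject to PI exception, so blood is also taken at a visit that is not one of the five research draws.

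The documents give no volume for the screening or safety labs and do not say whether the on-study safety labs are drawn within the 30 mL. No other cumulative volume appears.

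**The concern.** The limit is offered as a participant protection, and Section 12 lists blood drawing among the study's four major areas of risk. An IRB or safety board reading that section would take 40 mL as the total burden. Staff reading Section 6 and Table 1 would plan draws that go past it from the second research draw onward. A study team cannot comply with both statements, and anyone checking compliance would not know which one to apply.

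**Working it through.** **Inputs**

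- Limit L = 40 mL for the whole study, screening included (Section 12).
- Volume per research draw v, about 30 mL (Section 6).
- Number of research draws n = 5 (Section 6; five marks in Table 1).
- Screening and safety labs: 1 + 3 = 4 occasions (Table 1), volume not stated.

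**Step 1. Try to reproduce the 40 mL.** Total research blood = n x v = 5 x 30 = 150 mL. The stated 40 mL is not reproduced. The ratio is 150 / 40 = 3.75.

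**Step 2. Find where the limit is passed.** Cumulative research blood after draws 1 to 5 is 30, 60, 90, 120 and 150 mL. The second draw, at Baseline 2, takes it past 40 mL.

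**Step 3. Allow for the volume being approximate.**

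| mL per draw | After 2 draws | After 5 draws | Ratio to 40 mL |
|---|---|---|---|
| 20 | 40 | 100 | 2.5 |
| 25 | 50 | 125 | 3.1 |
| 30 | 60 | 150 | 3.75 |
| 35 | 70 | 175 | 4.4 |

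The second draw passes the limit whenever 2v > 40, that is, for any v above 20 mL. Five draws stay within the limit only if 5v ≤ 40, that is, v ≤ 8 mL, and then only with no screening blood at v = 8.

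**Step 4. Add screening and safety blood.** No volume is given, so this step is an assumption: 5 to 20 mL per lab occasion.

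- Screening only, with on-study safety labs inside the 30 mL: 150 + 5 = 155 to 150 + 20 = 170 mL, or 3.9 to 4.25 times the limit.
- All four lab occasions as separate blood: 150 + 4 x 5 = 170 to 150 + 4 x 20 = 230 mL, or 4.25 to 5.75 times the limit.

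**Step 5. Test the readings that would remove the conflict.**

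- *30 mL as the total over five visits.* This gives 30 / 5 = 6 mL per visit and leaves 40 - 30 = 10 mL for screening and three safety-lab sets, an average of 10 / 4 = 2.5 mL each. It fits numerically only if all of that blood comes to 10 mL or less.
- *40 mL as a limit per visit.* A 30 mL draw would fit, but the limit is expressly set over the course of the study.

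**The case against.** The best case for the plan is that Section 6 never says each visit or per visit. If 30 mL were the research total, 10 mL would remain and the limit could be met. The documents give no tube or safety-lab volumes, only 20 µl for the finger-prick CRP kit, so arithmetic alone does not exclude this reading. That much stands. The reading is nevertheless strained. The sentence fixes a morning window for a draw at named visits, which describes what happens on each occasion. Each draw also has to supply cytokines, tryptophan and kynurenine, mRNA, methylation and gene work. Even if the sponsor meant a total, the text would need to say so.

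Three stronger conclusions are tempting, and the documents do not support them.

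- *A reader might infer that the 40 mL figure is the error and is too low by at least 3.75-fold.* Nothing shows which figure was intended. Nor is 3.75 a floor: the draw volume is approximate, the ratio applies only to participants who complete all five draws, and the on-study safety labs may lie inside the 30 mL.
- *A reader might infer that obeying the limit would end sampling after Baseline 1 and lose the later biomarker samples and the Week 4 and Week 8 liver tests.* This is not derived. A team could draw less per visit, or give priority to safety labs. After one 30 mL draw, 10 mL less any screening blood would remain, and safety-lab volumes are unknown. Following the schedule instead would lose no samples at all.
- *A reader might infer that participants were given a wrong figure.* The consent pages are not in the text reviewed, and the risk description in Section 12 lists blood-draw risks without a volume.

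It is also fair to say that the statistical plan is untouched. Section 10 names no cytokine, kynurenine or expression outcome for Aims 1 and 2, and Section 11 does not depend on blood volume.

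**Conclusion.** The inconsistency is real. On the per-visit reading, the scheduled research blood passes the stated limit at the second draw, at about 60 mL against 40 mL, and this holds for any draw volume above 20 mL. A participant who completes all five draws gives about 150 mL, nominally 3.75 times the limit (about 3.1 times at 25 mL per draw), before screening blood of unstated volume.

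The conclusion rests on two assumptions: that the 30 mL applies at each named visit, and that the five marks in Table 1 are as extracted. It establishes that two current statements conflict. It does not establish which is right, that 150 mL would harm anyone, or that any planned analysis or the power would change. The passages should be reconciled because one of them is a stated protection that the plan's own schedule does not meet.

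**What to change.** Reconcile Description of Study Procedures and Table 1 in Section 6 with Adequacy of Protection Against Risks in Section 12:

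1. Total every scheduled draw once: five research draws, the screening labs, and the safety labs at Baseline 2, Week 4 and Week 8.
2. Say in Section 6 whether the 30 mL is per visit, and whether the on-study safety labs are taken within it or in addition to it.
3. State one per-visit volume and one study total that agree, and carry that total into the risk text in Section 12 and into any participant-facing document that gives a volume.

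Which figure governs is for the sponsor and the IRB. The cost is a wording amendment. Depending on that choice, either the stated total becomes less favourable or the per-visit volume changes. The sample size and the Aim 1 and Aim 2 analyses stay as they are.
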